### 7.7.2. Secondary Analysis/CCI

Analyses will be stratified by key demographic and clinical characteristics of interest (i.e., for HCP survey, by HCP type [e.g. physician, nurse, pharmacist]; for user survey, the location of practice where they receive CAB-LA (institution vs. community)) among users in the PSP database, should this data be available. For the user survey, a stratified analysis by prior oral PrEP use before starting CAB-LA will also be conducted. CCI

\$(vault:document\_date\_\_v)

Protocol for Non-Interventional Studies PASS Studies and Non-PASS Studies (4.0) March 2024

Template Doc ID: TMF-15706807

Parent Doc ID: VQD-SOP-066694

CCI

CCI

## 7.8. Quality Control and Quality Assurance

This study will be conducted according to local quality control processes. This procedure requires documented evidence that the study protocol has been correctly interpreted and executed.

This study will be conducted according to published best practices and guidance on the conduct of quantitative surveys, as well as Broadstreet Health Economics and Outcomes Research (HEOR) working practices to guide statistical analysis and validation. Details of these procedures are listed below, as are the details of a quality control (QC) independent review of final results to ensure that the study protocol has been correctly interpreted and executed.

Data will primarily be collected through securely hosted online surveys. CAB-LA users will have the option to complete a paper survey. The online surveys will be designed to not allow questions to be skipped (to avoid incomplete data); however, participants may select a “prefer not to answer” option, in particular for sensitive questions. Thus, incomplete questions are not expected for the online surveys; however, incomplete questions may occur for the paper survey. No imputation is planned for any missing data (incomplete questions or questions marked ‘prefer not to answer’). All data collected will be considered for the analysis, including for partially completed surveys. However, measures will be taken to optimize response rates (see section 7.5.2).

Additionally, the surveys will be designed to minimize the possibility of participants entering inappropriate responses. These design elements include using close-ended, true/false or multiple-choice options; allowing users to respond with “I’m not sure” or “Prefer not to answer” rather than participants entering erroneous responses; and restricting free text responses to only accept numeric data entries (where appropriate, e.g., entering participant age).

After the completion of the first surveys by HCPs and CAB-LA users, an analyst will assess response rate, as well as the quality of collected data. Data will be checked for missing, illogical, and inconsistent data, and automated data checks will also be conducted (e.g., range checking). Any implications regarding survey programming will be identified and

#{vault:document\_date\_\_v}

Protocol for Non-Interventional Studies PASS Studies and Non-PASS Studies (4.0) March 2024

Template Doc ID: TMF-15706807

Parent Doc ID: VQD-SOP-066694

implemented in the online surveys. Similar data checks will be re-conducted after survey recruitment has been closed. All modifications to the database will be clearly documented, and the study database will only be accessible to authorized study personnel.

During data analysis, certain data cleaning steps may be implemented. Numeric variables such as participant age will be reviewed for minimum and maximum, to identify any values that are likely to be data entry errors. Variables may be renamed from the raw survey data with shorter and more intuitive names for analysis. The list of variable names will be documented.

All analyses will undergo a QC review by an additional analyst not involved in the conduct of the original analyses. The QC analyst will review all programming code for population creation and results tables generated; will independently re-generate sample tables for each results section; and will verify the accuracy of all numeric values reported.

## 7.9. Limitations of the Research Methods

This study is subject to several limitations. Firstly, there is the potential for selection bias, given the voluntary nature of participation in the survey study, for both HCPs and CAB-LA users. Additionally, although efforts will be made to recruit a representative sample of different types of HCPs and CAB-LA users from different settings, the sample included in the study may not be representative of all HCPs and CAB-LA users. Further, given the self-reported nature of the data within this study, there are a number of additional biases to consider. First, self-reported data may be subject to reporting bias; second, recall bias may play a role in accurately remembering information, for example for questions related to CAB-LA user behaviours. Furthermore, given that the correct answers to the questions assessing knowledge can be identified by referring to the aRMMs, the consent form and survey instructions will clearly state that the intent of the survey is to assess general levels of knowledge and awareness, and that participants' responses cannot be linked back to them, in order to encourage participants to respond based on their own knowledge without referring to other materials. Lastly, CAB-LA users within the PSP may have important differences from those who are not in the PSP, therefore, the data may not be generalizable to all individuals who would receive CAB-LA. CCI

CCI

CCI

CCI

All limitations mentioned in this section will be included in the final study reports.

## 7.10. Other Aspects

In the event that KAB success thresholds are not reached, it will be important to identify possible reasons for failure and areas for potential intervention and improvement. By design, the survey will include questions that are not used in the scoring of KAB, but used to understand general use of aRMMs and potential reasons for suboptimal use. Free-text

#{vault:document\_date\_\_v}

Protocol for Non-Interventional Studies PASS Studies and Non-PASS Studies (4.0) March 2024

Template Doc ID: TMF-15706807

Parent Doc ID: VQD-SOP-066694

response options will be available in key questions in order to capture rich information that may inform strategies to improve the uptake of the optimal behaviours detailed in the aRMMs.

Since Apretude's approval in Canada in May 2024, the GSK/ViiV medical team has proactively developed programs for HCP education which can be leveraged if appropriate. These programs are based on a national learning needs assessment for HIV prevention and include other faculty-driven learning activities that provide key information on PrEP in general, but also on new modalities like Apretude. The educational focus is on acquiring knowledge (in-depth data review), but also on attitude and skills (data-light with focus on experience sharing and practical tips & tricks) to support HCPs in the safe use of Apretude. Another tool recently made available to HCPs is the Apretude Prevention Guide, which was developed by a group of experts across Canada, including infectious diseases specialists, family physicians, nurse practitioners and pharmacists specializing in HIV and PrEP. Of note, the details of the aRMMs as well as its resource page is provided to HCPs in this guide.

Based on the survey methodology, we expect that we will be able to identify whether the low level of success follows specific trends. For example, suboptimal behaviour in managing users who discontinue the regimen may be associated with a specific type of HCP, low levels of knowledge about adherence among users may be linked to specific regions, or systematic demographic differences may exist between participating groups, such as those with missing data compared to those who completed the survey. If so, we will focus our efforts on leveraging the existing education resources and adapting/tailoring them to appropriately addressing these gaps identified from this study.

It is anticipated that this corrective action plan will address any educational gaps that may be identified from the surveys.

Additionally, pilot testing will be conducted for the survey, to help ensure questions and response options, structure and programming, are best designed to minimize incomplete or inaccurate responses. If needed, the study protocol and survey questions may be re-evaluated and adapted for a re-assessment of KAB outcomes at 3 years.

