**Table 13. Levels of precision calculated by target sample size and proportion of correct responses**

	Correct response rate (%)				
Sample size	50	60	70	80	90
50	+/-13.9	+/-13.6	+/-12.7	+/-11.1	+/-8.3
100	+/-9.8	+/-9.6	+/-9.0	+/-7.8	+/-5.9
250	+/-6.2	+/-6.1	+/-5.7	+/-5.0	+/-3.7
500	+/-4.4	+/-4.3	+/-4.0	+/-3.5	+/-2.6

For binary % outcomes, based on the maximum variation assumption (p=0.50), the expected 95% confidence interval precision is +/- 9.8% for a sample size of 100 and +/- 6.2% for a sample size of 250.

The target sample size for the HCP survey is n=100 HCPs; the target sample size for the CAB-LA user survey is n=250. Thus, with respect to the primary study objective as reported by users, the maximum width of the expected confidence interval is +/- 9.8% for HCPs and +/- 6.2% for users.

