### Recruitment of HCPs

The recruitment strategy will target HCPs across different institutional and community settings representative of how care is offered in Canada, including but not limited to hospitals, outpatient clinics, pharmacies, community clinics, and private practices across Canada. Recruitment will be stratified by provider type. To adequately address objectives related to prescriber decision making, given that not all HCPs administering injections will be the ones making prescribing decisions, a minimum target of 50% prescribers has been set (i.e., recruitment for non-prescribing HCPs will be halted once the sample size reaches 50). HCP recruitment may take place through an established recruitment vendor for medical research (Medicys), with minimum targets for recruitment by prescriber status, clinical setting, and HCP type. Recruitment and survey materials for the secondary objectives will not contain language suggesting that the study was requested by HC.

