### Recruitment of CAB-LA Users

For the survey component of the study, CAB-LA users will be recruited using recruitment flyers/posters with a quick response (QR) code linked to the survey, displayed at different clinical settings where they access PrEP (for example, but not limited to hospitals, outpatient clinics, and pharmacies) across Canada. In addition, HCPs participating in the HCP survey may also direct CAB-LA users to the QR code for the survey. To reach target sample sizes and to ensure representativeness of the user sample, recruitment may additionally be conducted through Mediscys. Recruitment of CAB-LA users will be conducted in geographic regions where CAB-LA is publicly listed. As access expands across Canada, recruitment will also be expanded to ensure representation from all possible regions. The data will be analyzed by geographical location, with some regions anticipated to be grouped together based on available sample size (e.g., Western Canada). Recruitment and survey materials for the secondary objectives will not contain language suggesting that the study was requested by HC.

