HCPs will receive a one-time payment of \$350 upon completing the survey, while CAB-LA users will receive \$100. For the pilot testing, each of the 5 HCPs will be compensated \$350, and each of the 5 community members will receive \$100. Remuneration details will be provided in the consent form. For both surveys, unique survey links will be generated for each participant. The unique link will enable participants to save their progress and return to complete the survey at a later time, minimizing potential incomplete responses. In addition, checks will be in place to ensure that each link can only be used once to complete the survey and receive payment. Checks may include a combination of the following: 1) checking IP addresses; 2) checking for duplicate email addresses for payment; 3) checking for suspicious email addresses; 4) running PercentMatch statistical function assess the level of identical observations in the survey dataset; 5) checking for realistic survey completion times. Recruitment will continue for approximately five months, unless the closing criterion is met. The closing criterion for the survey is reaching the maximum sample size of 100 HCPs and 250 CAB-LA users.

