### **7.7.1. Primary Analysis**

#### **7.7.1.1. Main Analytical Approach**

##### **Primary Objectives**

The characteristics of HCPs and CAB-LA users will be summarized as frequencies and percentages (categorical variables) or as means, SD, medians and IQR (continuous variables). These will be summarized overall, by characteristics of interest (i.e., for HCP survey, by HCP type [e.g. physician, nurse, pharmacist]; for user survey, whether a user is a naïve or experienced with PrEP use, the location of practice where they receive CAB-LA (institution vs. community)) will be included in the stratified analyses.

The cross-sectional survey questions – addressing HCP and CAB-LA user knowledge, attitudes, and behaviours – will largely have categorical response options and will also be summarized as frequencies and percentages. By design, most survey data collected will be categorical. The proportion of correct and appropriate answers to key survey questions will be summarized, among those HCPs and CAB-LA users who provided responses to those questions (missing data will be summarized but not counted as a denominator in the proportions). The number and percentage of HCPs and CAB-LA users who have provided correct responses to knowledge questions will be summarized for each question, as well as the number and percentage of HCPs and CAB-LA users who have provided correct responses to at least 80% of all questions (target threshold for the study based on previous studies). Similarly, the number and percentage of HCPs and CAB-LA used who have provided responses indicative of optimal behaviour will be summarized for each question. Specific behaviours will be identified where less than 80% (or alternative thresholds) of participants reported optimal behaviour. Results will be presented overall for HCPs and CAB-LA users, as well as stratified by characteristics of interest (see section 7.7.2 for details). Free-text response options will be summarized for specific questions.

In addition to numeric results tables, customized visualizations will be developed to convey survey results for HCPs and CAB-LA users. These will include various histograms or bar charts to display the distribution of HCP and CAB-LA user responses for key survey items.

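### Section 7.10 expects the survey to show which HCP types or regions lie behind a missed threshold, but strata that may hold only 15 HCPs cannot separate moderate differences from chance

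*Protocol*

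**What the plan says.** Protocol section 7.10 sets out what happens if the success thresholds are not reached. It states: "Based on the survey methodology, we expect that we will be able to identify whether the low level of success follows specific trends". Its examples are suboptimal behaviour linked to one type of HCP and low adherence knowledge among users linked to particular regions. If such a pattern appears, "we will focus our efforts on leveraging the existing education resources and adapting/tailoring them to appropriately addressing these gaps identified from this study".

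The design behind that expectation is as follows.

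- **Sample size (7.5.1).** "The target sample size for the HCP survey is n=100 HCPs; the target sample size for the CAB-LA user survey is n=250". Table 13 gives half-widths for n=50, 100, 250 and 500. The text applies only the n=100 and n=250 rows, each to a whole survey.
- **Cap (7.5.2, Logistics and Monitoring).** Recruitment closes on "reaching the maximum sample size of 100 HCPs and 250 CAB-LA users", so the strata cannot grow by over-recruiting.
- **HCP strata (7.5.2 and Table 14).** Recruitment proceeds "with minimum targets for recruitment by prescriber status, clinical setting, and HCP type". The minimum is 15 each for physicians, nurses and pharmacists.
- **Regions (7.5.2, Recruitment of CAB-LA Users).** No minimum is set. "The data will be analyzed by geographical location, with some regions anticipated to be grouped together based on available sample size".
- **Reporting (7.7 and 7.7.1.1).** "Results will be presented overall for HCPs and CAB-LA users, as well as stratified by characteristics of interest". Section 7.7 presents binary and categorical outcomes as numbers and percentages, and names 95% confidence intervals only for continuous endpoints.

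**The concern.** Section 7.10 attributes a capability to the survey and makes corrective action in a Health Canada-mandated study follow from it. Nothing in the protocol derives that capability. The sample-size argument concerns overall percentages, whereas the capability concerns differences between strata that may be a small fraction of the total.

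Two errors are possible. Types with the same true success rate may look different in the tables, and education is then tailored to a pattern that is noise. Or one type may have a real deficit of moderate size that does not stand out, and it gets no particular attention. Bare percentages give the reader no means of telling these situations apart.

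The protocol's own HCP example may involve strata below 15. In Table 5, counselling of users who are considering discontinuation is a prescribers-only item. Section 7.2 notes that not all nurses and pharmacists can prescribe. Table 14 sets a floor of 50 prescribers overall but none within nurses or pharmacists.

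**Working it through.** **Inputs.** n=100 HCPs and n=250 users (7.5.1); 15 per HCP type (Table 14); 70% population cut-off (7.3.2, assessment of success); normal approximation to the binomial (7.5.1). The true rates and the splits across HCP types below are assumptions.

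**1. The plan's own figure.** The half-width is 1.96 × √(p(1−p)/n). At p=0.50:
- n=100: 1.96 × √(0.25/100) = 9.8 points
- n=250: 1.96 × √(0.25/250) = 6.2 points

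Both agree with the text ("based on the maximum variation assumption (p=0.50), the expected 95% confidence interval precision is +/- 9.8% for a sample size of 100"), and all 20 cells of Table 13 reproduce to one decimal.

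**2. The same formula at stratum size.**

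| n | p=0.50 | p=0.70 | p=0.80 |
|---|---|---|---|
| 15 (Table 14 floor) | ±25.3 | ±23.2 | ±20.2 |
| 33 (about equal split) | ±17.1 | ±15.6 | ±13.6 |
| 100 (all HCPs) | ±9.8 | ±9.0 | ±7.8 |

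At n=15 the interval is √(100/15) = 2.6 times as wide as for all HCPs. For example, 9 successes in 15 (60%) has an exact 95% interval of 32.3% to 83.7%, which covers both clear failure and clear success against 70%.

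**3. Interval for a difference.** The half-width is 1.96 × √(p₁(1−p₁)/n₁ + p₂(1−p₂)/n₂). For 80% versus 60%:
- 15 vs 15: 1.96 × √(0.16/15 + 0.24/15) = 32.0 points
- 33 vs 33: 1.96 × √(0.16/33 + 0.24/33) = 21.6 points

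Both exceed the 20-point difference itself.

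**4. Chance gaps with no true difference.** Three HCP types share one true success rate. The table gives the probability that the best and worst observed rates differ by 20 points or more.

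| Split | True rate 65% | True rate 70% |
|---|---|---|
| 15/15/70 | 43% | 40% |
| 15/42/43 | 28% | 25% |
| 34/33/33 | 19% | 17% |

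With discrete counts the 15/15/70 figure depends on including gaps of exactly 20 points. Strictly above 20 points it is 31% at a true rate of 65%. The 34/33/33 figure does not change.

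**5. Power for a true 80% versus 60%.** Two-sided 5% pooled two-proportion z test, exact enumeration:
- 15 vs 15: 23%
- 15 vs 70: 41% if the small group is at 60%, 31% if the large group is
- 33 vs 33: 44%

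**6. What could be seen.** The gap below a 70% reference that is detectable with 80% power (normal-approximation formula) is about 49 points for 15 vs 15, 38 for 15 vs the other 85, and 34 for 33 vs 33. Detecting 70% versus 50% needs 93 per group, almost the whole HCP sample for each type.

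**7. Regions.** The protocol gives no regional n. If the 250 users were spread like the 159 support-program sites in section 7.2 (an assumption), half-widths at 70% would be about ±8.1 for Ontario (n≈123), ±11.3 for Quebec (n≈63), ±12.9 for the western provinces (n≈49) and ±23.9 for the Atlantic provinces (n≈14). Large regions could be read with fair precision and small ones could not.

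**The case against.** The strongest reply is that section 7.10 is hedged and the study is descriptive. It speaks of an expectation and of patterns that may exist. It also draws on unscored questions and free text to understand reasons, and section 7.10 leaves open a re-assessment at 3 years. Fifteen is a floor: with 100 HCPs the largest type has at least 34, and the live dashboard allows recruitment to be steered. Interval columns are commonly specified in a statistical analysis plan, which is not shown here, and 7.5.1 already speaks of confidence intervals around the estimates.

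Much of this stands, and it rules out several stronger readings that a reader might infer.

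- *Stratified results carry no exploratory caveat.* This cannot be shown. The heading and text of 7.7.2 and parts of 7.9 are redacted.
- *Intervals will not be produced for strata.* Section 7.7 does not name them for binary outcomes, but that does not prove they are absent from the full plan.
- *Education will be confined to one subgroup.* The text speaks of focusing and tailoring existing resources. It does not say other groups are left out.
- *Reading many items by stratum gives a known false-positive rate.* The protocol plans no item-level tests, so such a figure would rest on an analysis nobody proposed.
- *Regional strata are as small as HCP strata.* Their size is unknown.

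What the reply does not supply is any basis for the expectation itself. Even the most favourable equal split misses a true 20-point deficit more often than it finds it. Free text may explain why a group did poorly, but it does not establish that the group differs.

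**Conclusion.** The point holds in a limited form. Section 7.10 states a capability that the design lacks for moderate differences, of about 20 points, between HCP types. At the guaranteed stratum size the half-width at 70% is about 23 points. With equal true rates of 65%, a gap of 20 points or more appears in 19% to 43% of surveys, and power for 80% versus 60% runs from 23% to 44%. Gaps of roughly 35 to 50 points could be recognised, so it would be too strong to say that the survey can identify nothing.

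The figures assume independent respondents, the stated true rates and splits between 15/15/70 and 34/33/33. Prescriber-only items could make strata smaller than 15 and the position worse. For regions the conclusion is only that precision is undetermined. Because the wording steers corrective action in a mandated study and the change is nearly free, it should be made, but it does not threaten the primary overall estimates.

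**What to change.** - **7.5.1:** add the expected half-width at n=15 and about n=33 (at 70%, ±23.2 and ±15.6 points), and say that regional precision depends on the numbers recruited.
- **7.7 and 7.7.2:** for each stratum, report n and a 95% confidence interval for the domain-level success rate, and a 95% confidence interval for differences between strata.
- **7.10:** replace the expectation with a statement that subgroup patterns are hypothesis-generating, can reveal only large differences, and will be read with their intervals before they inform any tailoring.

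No formal testing or multiplicity adjustment is needed in a descriptive study, and who receives corrective education remains a programme decision. The cost is a few sentences and a few extra columns in the shell tables. The downside is that section 7.10 promises less precise targeting.
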